7. RESEARCH QUESTIONS

- In adults living in Colombia with co-existing physical and mental non-communicable diseases, does the DD+ intervention, compared to usual care, lead to quality of life improvement?
- Is the DD+ intervention implementable in the local Colombian context for patients with co-existing physical and mental NCDs, considering identified barriers and facilitators, and in terms of its feasibility, appropriateness, acceptability, adoption, and fidelity?
- In adults living in Colombia with co-existing physical and mental non-communicable diseases, does the DD+ intervention, compared to usual care, lead to enhancing social functioning and service utilisation, and in reducing depressive and anxiety symptoms?
- In adults living in Colombia with co-existing physical and mental non-communicable diseases, does the DD+ intervention, compared to usual care, lead to an improvement of clinical outcomes for diabetes, obesity or HBP?

- Does the effect of DD+ intervention in patients with co-occurring physical and mental non-communicable diseases at 6 months remain stable when the intervention frequency is reduced to every two months for the subsequent 6 months?
- What is the additional cost and cost-effectiveness of implementing and delivering the patient-centred, solution-focused intervention DD+ as part of usual care for adults with co-existing physical and mental non-communicable diseases in Colombia?

8. OBJECTIVES AND OUTCOME MEASURES

Table 1. Objectives and outcome measures

| Objectives | Outcome Measures | Timepoints of evaluation |
|--|---|--|
| Primary Objective Evaluate the effectiveness of DD+ intervention for improving QoL of patients with co-existing physical and mental NCDs in Colombia. | Change in QoL at 6 months measured by MANSA. | - Baseline Assessment -6-month follow-up- |
| Secondary Objective (Implementation) Analyse the implementation context for DD + intervention for patients with co-existing physical and mental NCD to improve their QoL in local Colombian contexts. Through the following specific objectives: 
 - Identify barriers and facilitators for implementation of DD + intervention for patients with physical and mental NCD to improve their QoL in local Colombian contexts. - Assess the feasibility of DD+ intervention for | 
 - Barriers and facilitators for implementation through qualitative interviews. - Feasibility measured through qualitative interviews. - Feasibility of Intervention Measure (FIM) - Feasibility measured as completion proportion (participants who agreed to participate, consented to do so, and were allocated to active treatment and completed the intervention as planned in relation to all those who agreed to participate and consented to do so) - Appropriateness measured through qualitative interviews. - Intervention Appropriateness Measure (IAM) | - Baseline Assessment -6-month follow-up- |

| | | |
|---|---|---|
| 
patients with physical and mental NCD to improve their QoL in local Colombian contexts.
 
 - Assess the Appropriateness of DD + intervention for patients with physical and mental NCD to improve their QoL in local Colombian contexts. - Assess the acceptability of DD + intervention for patients with physical and mental NCD to improve their QoL in local Colombian contexts. - Assess the adoption of DD + intervention for patients with physical and mental NCD to improve their QoL in local Colombian contexts. - Assess the fidelity of DD + intervention for patients with physical and mental NCD to improve their QoL in local Colombian contexts. | 
 - Acceptability measured through qualitative interviews. - Acceptability of Intervention Measure (AIM) | |
| 
Secondary Objective (Effectiveness)
 
Evaluate the effectiveness of the DD+ intervention in enhancing social functioning and in reducing depressive symptoms and anxiety among individuals with co-existing physical and mental NCDs in Colombia.
 | 
 - Change in Social Functioning measured with Objective Social Outcomes Index (SIX) - Change in depressive symptoms, measured with Patient Health Questionnaire-8 (PHQ-8) - Change in anxiety symptoms, measured with Generalised Anxiety Disorder- 7(GAD-7) | 
 - Baseline Assessment -6-month follow-up - 12-month follow-up |
| 
Secondary Objective (Effectiveness)
 | 
 - Change in HbA1c measured through a capillary sample. | 
 - Baseline Assessment |

| | | |
|--|---|---|
| Evaluate the effectiveness of DD+ intervention in the reduction of HbA1c, systolic mmHg, diastolic mmHg, abdominal circumference and BMI | 
 - Change in systolic/diastolic mmHg measured through an automatic blood pressure cuff - Change in abdominal circumference measured with standard measuring tape | 
 -6-month follow-up- - 12-month follow-up |
| Secondary Objective (Effectiveness) Evaluate the stability of treatment when reducing the frequency of DD+ visits (bimonthly visits in the 6 to 12-month period) | 
 - Change in QoL measured by MANSA. | -12-month follow-up |
| Secondary Objective (Cost effectiveness) Assess the additional cost and cost-effectiveness for implementation and delivery of patient-centred solution-focused intervention with DD+ into usual care for adults with co-existing physical and mental NCDs in Colombia. | 
 - Cost in USD - Cost per Quality Adjusted Life Year (QALYs) gained - Changes in clinical variables (blood pressure, glycosylated haemoglobin, body weight and waist circumference). | 
 -6-month follow-up- - 12-month follow-up |

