15.2. Sample Size Determination

The sample size calculation for this study will be based on parameters derived from previous DIALOG+ trials (35). A standard deviation of 0.9 for the MANSA and a correlation of 0.4 between baseline and follow-up measurements will be assumed, while an effect size of 0.4 points on the MANSA will be considered the minimal clinically important difference (MCID) for quality of life in this patient population. Based on these parameters, a total of 90 participants per group will be required to achieve 90% power at the 5% two-sided significance level. To account for an anticipated 20% attrition rate, the final sample size will be set at 226 participants (113 per group).

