15.9. Secondary Objective (Effectiveness)

Mixed-effects models will be used to evaluate the effect of the intervention on the secondary outcomes (see **Table 1**) at 6- and 12-month follow-up assessments. Analyses will be conducted under the intention-to-treat principle. Each model will include fixed effects for treatment group (intervention vs control), time, the baseline score of the corresponding outcome, and other relevant baseline covariates. A random effect for clinical professional group (cluster) will be included to account for intragroup correlation. The models will report adjusted mean differences between groups, with corresponding 95% confidence intervals (CIs) and p-values.

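### The secondary objective asks whether the 6-month MANSA effect is maintained to 12 months, but the analysis in Section 15.9 never estimates the change in effect

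*Protocol*

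**What the plan says.** Section 7 of the Protocol, fifth question, asks whether the effect seen at 6 months will "remain stable when the intervention frequency is reduced to every two months for the subsequent 6 months". Table 1 in Section 8 turns this into a secondary effectiveness objective, "Evaluate the stability of treatment when reducing the frequency of DD+ visits (bimonthly visits in the 6 to 12-month period"). Its outcome is change in MANSA, and the only timepoint listed for it is 12 months. Table 1 does not say what would count as stable.

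Section 15.9 is the only analysis text that covers this objective. On the model it says: "Each model will include fixed effects for treatment group (intervention vs control), time, the baseline score of the corresponding outcome, and other relevant baseline covariates". Clinicians enter as a random cluster term. On the output it says: "The models will report adjusted mean differences between groups, with corresponding 95% confidence intervals (CIs) and p-values". No interaction of group with time is listed, and no comparison of the 12-month with the 6-month difference.

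Section 15.2 sizes the trial for a single superiority comparison on MANSA and states that "an effect size of 0.4 points on the MANSA will be considered the minimal clinically important difference (MCID").

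**The concern.** A question about maintained effect concerns the difference between two treatment effects: DD+ minus control at 12 months, less DD+ minus control at 6 months. The analysis in Section 15.9 yields something else, a difference between arms compared with zero.

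The possible results do not answer the question. A significant difference between arms shows that there is some effect, and this can hold after much of the 6-month effect has gone. A non-significant difference at 12 months shows neither that the effect was lost nor that it was kept. With main effects only, the model goes further and assumes that the arm difference is the same at both visits, so it builds in the very thing the objective sets out to examine.

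At stake is the trial's own question about less frequent delivery. Section 6 says the trial should inform scale-up and long-term sustainability, and whether the effect lasts under fewer sessions bears on that.

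**Working it through.** **Inputs from Section 15.2.** "A standard deviation of 0.9 for the MANSA and a correlation of 0.4 between baseline and follow-up measurements will be assumed"; a target difference of 0.4 points; "a total of 90 participants per group will be required to achieve 90% power at the 5% two-sided significance level"; and, on dropout, "To account for an anticipated 20% attrition rate, the final sample size will be set at 226 participants (113 per group").

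**Assumed.** The Protocol gives no correlation between 6-month and 12-month MANSA, so r is varied from 0.4 to 0.8. The baseline correlation of 0.4 is taken to apply at both follow-ups. Clustering by clinician is ignored, and the standard error is taken to allow correctly for two measurements on the same person.

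**Step 1: reproduce the sample size.** Baseline-adjusted variance = 0.81 × (1 − 0.4²) = 0.81 × 0.84 = 0.6804. n per arm = 2 × (1.96 + 1.2816)² × 0.6804 / 0.4² = 89.4, so 90. With 20% attrition, 90 / 0.8 = 112.5, so 113. The plan's figures are confirmed.

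**Step 2: the model as listed, when half the effect is lost.** Let the true effect be 0.4 at 6 months and 0.2 at 12 months. A single common group effect then estimates the average, 0.3.

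- SE(pooled) = √[2 × 0.81 × ((1 + r)/2 − 0.16) / 90]
- P(significant) = Φ(0.3/SE − 1.96)

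**Step 3: the quantity the objective needs.** This is the 12-minus-6-month difference in effect.

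- SE(change) = √[2 × 2 × 0.81 × (1 − r) / 90]
- 95% CI half-width = 1.96 × SE(change)

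| r | SE(pooled) | P(significant) | SE(change) | CI half-width |
|---|---|---|---|---|
| 0.4 | 0.099 | 86% | 0.147 | 0.29 |
| 0.6 | 0.107 | 80% | 0.120 | 0.24 |
| 0.8 | 0.115 | 74% | 0.085 | 0.17 |

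**Step 4: a separate 12-month comparison, if Section 15.9 is read that way.** SE = √(2 × 0.6804 / 90) = 0.123. With a true 12-month effect of 0.2, P(significant) = Φ(0.2/0.123 − 1.96) = 37%. In either outcome the result says only whether an effect is detectable at 12 months.

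**Step 5: what a formal claim would need.** For illustration, take a margin of −0.2 (half of 0.4), one-sided 2.5% and no true loss. With 90 per arm the power is Φ(0.2/SE(change) − 1.96) = 27%, 38% and 65% at r = 0.4, 0.6 and 0.8. For 80% power, 382, 255 and 128 evaluable per arm would be needed.

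**The case against.** The strongest case against is that a margin or decision rule usually belongs in the SAP, which is not at hand, and that evaluating stability can mean estimating it. Section 9 states no hypothesis about stability, and Section 15.9 does promise confidence intervals. Much of this stands: the absence of a margin is not a fault here. It does not remove the point, because Section 15.9 names its model terms and its reported quantity, and the promised intervals are for the arm difference, not for the change in that difference.

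It can also be said that Section 15.9 refers to effects at 6 and 12 months, which may intend separate differences at each visit. That is a fair reading, and under it the 74% to 86% figure does not apply. The contrast between the two visits would still be missing.

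Three stronger readings are tempting and are not supported:

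- A reader might infer that the plan will treat a non-significant result as proof of stability. Nowhere does the Protocol say so.
- A reader might conclude that a loss of half the effect would pass as stable in roughly 35% to 73% of trials. Those are the rates at which a test of the 12-versus-6-month change would be non-significant, and the plan contains no such test. For the same reason, the argument that more dropout favours a finding of stability does not apply to the analysis as written.
- A reader might take −0.2 as the right margin. It has no basis in the Protocol beyond halving the MCID, and it need not protect half of the observed effect. A just-significant 6-month difference is 1.96 × 0.123 = 0.24, and a loss of just under 0.2 would leave about 0.04, or one sixth.

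**Conclusion.** The objective and its analysis do not match. Followed as written, Section 15.9 produces no estimate of how the DD+ effect on MANSA changes between 6 and 12 months, so it cannot answer the fifth research question whichever way its p-values fall. With a common group effect, a loss of half the target effect coexists with a significant pooled result in about 74% to 86% of trials. That range depends on the assumed correlation of 0.4 to 0.8, on 90 evaluable per arm with SD 0.9, and on ignoring clinician clustering.

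This is a secondary objective. The 6-month primary analysis and its sample size are untouched. The point should be corrected, but it does not threaten the trial's main conclusion.

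**What to change.** In Section 15.9, add for the stability objective:

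- a group-by-time term in the MANSA model;
- the DD+ minus control difference at 12 months minus that at 6 months, with its two-sided 95% CI, reported beside the 6-month and 12-month differences;
- a statement that the objective is one of estimation, and that neither a non-significant change nor a significant 12-month difference alone will be described as stability.

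In Table 1, list the 6-month timepoint for this objective as well. If the sponsor wants a formal claim that the effect is retained, it should set and justify its own margin in advance.

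The same edit should reconcile the maintenance schedule: Sections 7 and 8 describe sessions every two months, while Section 12.10 places the two maintenance visits at 90-day intervals. The objective should name the schedule that is actually studied.

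The cost is a few sentences, with no new data or patients. The drawback is precision: with a CI half-width of about 0.17 to 0.29 points against a target effect of 0.4, the likely output is an estimate with its interval, not a confirmed claim of stability.

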| | 
situation, envisioning a preferred future, exploring available options, and agreeing on concrete actions. This structured dialogue promotes solution-focused care, helps patients draw on personal and external resources, and enables progress to be tracked digitally across sessions.
 
By embedding these features, DD+ aims to enhance patient engagement, improve continuity of care, and address both physical and mental health needs in individuals living with non-communicable diseases (NCDs).
 | | |
|----------------------------|--|---|--|
| Comparator/Control | Usual routine care as provided by each healthcare centre. | | |
| Planned Study Period | 
15 months
 
Recruitment 3 months
 
Intervention Phase: 6 months – monthly intervention
 
Maintenance Phase: 9- and 12-month intervention
 
Follow-up: 6 and 12 months
 | | |
| Planned Recruitment period | 
Start date: March 2026 (or if REC/IRB approval is obtained before this date in 2026).
 
End date: July 2027
 | | |
| | Objectives | Outcome Measures | Timepoints |
| Primary (Effectiveness) | Evaluate the effectiveness of DD+ intervention for improving QoL of patients with co-existing physical and mental NCDs in Colombia. | Change in QoL at 6 months measured by MANSA. | 
 - Baseline Assessment -6-month follow-up- |
| Secondary (Implementation) | Analyse the implementation context for DD + intervention for patients with co-existing physical and mental NCD to improve their QoL in local Colombian contexts. | 
 - Barriers and facilitators for implementation through qualitative interviews. - Feasibility measured through qualitative interviews. - Feasibility of Intervention Measure (FIM) - Feasibility measured as completion proportion (participants who agreed to participate, consented to do so, and were allocated to active treatment and completed the intervention as planned in relation to all those who agreed to | 
 - Baseline Assessment -6-month follow-up- |

| | | | |
|--|--|--|--|
| | | 
participate and consented to do so)
 
 - Appropriateness measured through qualitative interviews. - Intervention Appropriateness Measure (IAM) - Acceptability measured through qualitative interviews. - Acceptability of Intervention Measure (AIM) | |
|--|--|--|--|

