At visit 6, a researcher will update the CSRI with participants, either at the health centre during the DD+ intervention visit or by phone within five days after the visit.

Visits 3 to 8 – Control group follow-up

Participants allocated to the control group will be followed up on monthly by phone call to assess any health events, and to remind the 6-month follow-up visit.

Visit 9- Main and secondary 6-month outcome assessment.

Within 30 days after Visit 8, a researcher will schedule Visit 9 with participants. The researcher will complete the clinical scales described in Table 1 through patient interviews. Also, HbA1c, HBP and abdominal circumference will be reassessed. For the qualitative implementation assessment, twenty-four patients will be sampled and interviewed as defined in Section 13. Semi-structured interviews will be audio-recorded and are expected to last between 30 and 60 minutes.

Visit 10 and 11- Maintenance period intervention visits

At 90 (± 10) days from visit 9 (visit 10) and 90 (± 10) days from visit 10 (visit 11), participants in the intervention arm will go through the DD+ intervention.

Visits 10 and 11 – Control group follow-up

At 90 (± 10) days from visit 9(visit 10) and 90 (± 10) days from visit 10 (visit 11), participants in the control arm will receive a follow-up phone call.

Visit 12- Main and secondary 12-month outcome assessment

At ± 10 days after visit 11, a researcher will schedule visit 12 with participants. The researcher will complete clinical scales and CSRI through patient interviews. Visit 12 will be the last study visit.

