12.12. Early Discontinuation/Withdrawal of Participants

During the course of the study, a participant may choose to withdraw early from the study treatment at any time. This may happen for several reasons, including but not limited to:

- The occurrence of what the participant perceives as an intolerable Adverse Events (AE).
- Inability to comply with study procedures
- Participant decision

Any participant will be given three options when withdrawing from the study:

1. Withdrawal from active follow-up/ treatment and further communication, but allow the study team to continue to access their medical records and any relevant clinical data that is recorded as part of routine standard of care.
2. Withdrawal from active follow-up/ treatment and further communication, keeping the consent to use data already collected up to the time of withdrawal.
3. Complete withdrawal from the study, including data and samples collected up until the point of withdrawal. The data and samples already collected would not be used in the final study analysis. However, if the analysis of their data or samples has already been integrated into interim or final analysis, it should be explained to the participant.

In addition, the Investigator may discontinue a participant from the study treatment at any time if the Investigator considers it necessary for any reason, including, but not limited to:

- Ineligibility (either arising during the study or retrospectively having been overlooked at screening)
- Significant protocol deviation
- Significant non-compliance with treatment regimen or study requirements
- Clinical decision

For any of the aforementioned situations, the type of withdrawal and reason for withdrawal will be recorded in each participant's CRF.

If the participant withdraws due to an adverse event, the researcher will arrange fortnightly telephone calls until the adverse event has been resolved or the end-of-study definition is reached. Clinical management of the participant will be the responsibility of the health system the participant is affiliated with. As stated elsewhere, the security record of the intervention does not foresee AE related to the intervention or serious adverse event (SAE).

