12.13. Definition of End of Study

The end of the study is defined as the date when the last patient completes Visit 10. All IRBs/RECs that have approved the study will be informed of the end of the study, site closure, and archiving procedures initiated.

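### The stability objective names two-monthly maintenance sessions but the schedule gives one every 90 days; separately, section 12.13 ends the study at Visit 10, before the 12-month outcome visit (Visit 12)

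*Protocol*

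**What the plan says.** **Maintenance interval.** Section 7 of the Protocol asks whether the 6-month effect holds "when the intervention frequency is reduced to every two months for the subsequent 6 months". The matching secondary objective in Table 1 (section 8) describes the regimen as "bimonthly visits in the 6 to 12-month period". The operational text differs. The Synopsis gives "Maintenance Phase: 9- and 12-month intervention", and Table 2 places each maintenance session 90 days after the preceding visit. Section 12.10 sets Visit 10 at 90 (±10) days from Visit 9 and, for Visit 11, 90 (±10) "days from visit 10 (visit 11), participants in the intervention arm will go through the DD+ intervention". Visit 12, the 12-month assessment, is set within 10 days of Visit 11.

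**End of study.** Section 12.13 states: "The end of the study is defined as the date when the last patient completes Visit 10". It goes on to say that the ethics committees will be "informed of the end of the study, site closure, and archiving procedures initiated". In Table 2, Visit 10 is the first maintenance session (month 9) and Visit 12 is the 12-month assessment. Section 12.10 says "Visit 12 will be the last study visit". Section 12.12 uses the same definition as a stopping point for participants who withdraw because of an adverse event: they receive "fortnightly telephone calls until the adverse event has been resolved or the end-of-study definition is reached".

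**The concern.** The session interval is the exposure that the stability objective exists to test. If the objective names one interval and the trial delivers another, a 12-month report worded from the objective would claim stability under a regimen that no participant received. The interval also sets how many sessions are delivered and costed in the 12-month economic base case.

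The end-of-study definition triggers other actions: notification of ethics committees, site closure, archiving, and the end of calls to participants who withdrew for an adverse event. The minimum retention period (section 17.3) and the deadline for posting results (section 21.7) also run from the end of the trial. Read literally, section 12.13 starts all of these before the 12-month outcomes are complete. Those outcomes include MANSA, PHQ-8, GAD-7, SIX, HbA1c and blood pressure, and the EQ-5D and CSRI data needed for 12-month QALYs and costs.

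**Working it through.** **What is not affected.** Section 15.2 assumes SD 0.9, correlation 0.4, difference 0.4, 90% power and 5% two-sided alpha. The baseline-adjusted variance is 0.9² × (1 − 0.4²) = 0.6804, which gives 90 per group (power 90.2%). Then 90 / 0.8 = 112.5, rounded up to 113 per group, 226 in total. This reproduces the protocol, and neither point below enters it.

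**Maintenance dose.** Inputs: a 60-day interval from sections 7 and 8; a 90 (±10)-day interval from Table 2 and section 12.10; a nominal maintenance period of 90 + 90 = 180 days after Visit 9.

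| | Two-monthly (sections 7 and 8) | As scheduled (Synopsis, Table 2, 12.10) |
|---|---|---|
| Sessions in 180 days | 180 / 60 = 3 (days 60, 120, 180) | 180 / 90 = 2 (days 90, 180) |
| Sessions more than 10 days before day 180 | 2 (days 60, 120) | 1 (day 90) |
| Total sessions with the six monthly ones | 6 + 3 = 9 | 6 + 2 = 8 |

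The visit window does not reconcile the two, because the shortest permitted gap is 90 − 10 = 80 days. Nor does the ambiguity of the word bimonthly. Section 7 settles it as every two months, and the other reading (twice a month) is further still from 90 days.

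**End-of-study gap.** Visit 11 follows Visit 10 by 90 ± 10 days, and Visit 12 is within ±10 days of Visit 11.

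- Nominal gap from Visit 10 to Visit 12: 90 days.
- Shortest: 80 − 10 = 70 days.
- Longest: 100 + 10 = 110 days.

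**Visits still due on that date.** Assume even accrual, the same visit timing for everyone and no attrition. The share of participants with Visit 12 outstanding when the last patient completes Visit 10 is min(1, gap / accrual length).

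| Accrual | Shortest gap (70 days) | Longest gap (110 days) |
|---|---|---|
| 90 days (the stated 3 months) | 70 / 90 = 78% (176 of 226) | above 1, so capped at 100% (226) |
| 487 to 517 days (March 2026 to July 2027) | 70 / 517 = 14% (31 of 226) | 110 / 487 = 23% (51 of 226) |

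At the nominal 90-day gap and 90-day accrual, the share is 90 / 90 = 100%. The second row is shown because the Synopsis lists those dates as the recruitment period, although it also gives 3 months of recruitment within a 15-month study.

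**The case against.** - **Sites would not be misled.** The Synopsis, Table 2 and section 12.10 agree on 90 days, and the analysis in section 15.9 has no term for session interval, so the estimate is the same under either wording. This stands for conduct and estimation. It does not rescue the interpretation, since the objective still attaches that estimate to a different regimen.
- **A sparser schedule is a conservative test.** If benefit persists at 90-day spacing, one may argue that it would persist at 60-day spacing. That is a reasonable inference after a positive result, but it is an inference and not what the trial observes. A loss of effect would leave the two-monthly question open.
- **Visit 10 is probably an uncorrected visit number.** Section 12.10 and every reference to 12-month data point to Visit 12, and section 12.13 does not cancel any visit. This is likely correct, and the percentages above are visits still due, not data expected to be lost. But section 12.13 is the governing definition for notification, closure and archiving, and it cannot hold together with section 12.10.
- **The longer accrual period may not be real.** March 2026 to July 2027 sits better with the whole study than with recruitment. This is fair. The 14% to 23% row is a bound, and the 3-month row follows the stated recruitment length.
- **The intended interval is assumed.** If the sponsor wanted two-monthly sessions, the correction would add a session. The protocol does not say which was meant, but three operational places agree on 90 days.
- **The safety consequence is small.** It is limited to calls after withdrawal for an unresolved adverse event. Follow-up of serious adverse events (section 14.1.3) runs to resolution and is untouched.

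**Conclusion.** Both contradictions are in the current text and both should be corrected. The stability objective names a regimen of three sessions over six months. The trial delivers two, with one clearly before the 12-month assessment, so the 12-month result supports a statement about roughly three-monthly sessions only. Section 12.13 closes the study nominally 90 days (70 to 110) before the last patient's Visit 12. At that date 78% to 100% of participants would still have Visit 12 due, given even accrual over the stated 3 months, common visit timing and no attrition. If accrual really ran from March 2026 to July 2027, the share would be about 14% to 23%. The size of the gap does not depend on accrual. The effects are confined to a secondary objective and to trial conduct after month 6.

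**What to change.** 1. In section 7 and in Table 1 (section 8), replace the two-monthly description with sessions at 90-day intervals, at months 9 and 12, as already scheduled. Word the 12-month stability conclusion for that interval.
2. In section 12.13, define the end of study as the date on which the last participant completes Visit 12.

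The cost is a wording amendment in three places before recruitment. No visits are added, and the sample size and primary analysis do not change. If the sponsor in fact intends two-monthly sessions, the schedule must change instead: a third maintenance session, a matching control call, revised text in the Synopsis, Table 2 and section 12.10, and a higher delivery cost.
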